11.1.2 Stiffness

Passive stiffness total, stretch reflex mediated stiffness and EMG amplitude in the hamstrings will be analysed with a Bonferroni correction (n=3 variables p=0.05/3=0.0015).

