7.3.2 Stiffness (B)

B1. Passive Stiffness

Knee flexor passive stiffness will be assessed with the Biodex system, using six, 15-degree amplitude stretches, from a starting position of 90 degrees knee flexion and at a speed of 5 degrees per seconds. Stretches will be separated by between 2-5 seconds, to allow the muscle to relax between each stretch. EMG monitoring will ensure that the muscle is relaxed before a stretch is applied.

B.2 Stretch Mediated Stiffness

Knee Flexor stretch mediated stiffness will also be assessed with the Biodex system using six, 15-degree amplitude stretches, from a starting position of 90 degrees knee flexion. In order to bring about a stretch reflex mediated muscle response this stretch will be carried out at a speed of 75 degrees per second. Again, stretches will be separated by between 2-5 seconds, to allow the muscle to relax between each stretch and EMG monitoring applied to ensure the muscle is relaxed before a stretch is applied.

Total Stiffness

Total Stiffness will be determined from the fast stretch, following removal of torque due to the weight of the leg (estimated via anthropometric data). Offline analysis in Matlab[™] will determine the average torque and position in the 300 ms prior to the stretch onset and 300 ms period immediately after stretch offset and manipulandum as:

Stiffness = $\frac{Change in torque}{Change in position}$

Passive stiffness (assessed following the 5 deg/s stretch) and total stiffness following the fast stretch will be determined. Stretch Mediated stiffness wil be determined as:

Stretch Mediated stiffness = Total stiffness (fast stretch)- passive stiffness.

Mean EMG amplitude in the hamstrings following the mediated stretch stiffness will be determined. Here the EMG signal will be rectified and the onset and offset of EMG activation determined as the point the signal goes above and below a level (mean baseline period + 4 standard deviations). In total four variables will be assessed (Passive Stiffness, total stiffness, stretch mediated stiffness and EMG amplitude).

An exploratory assessment of activation of the gastrocnemius during muscle stretch tests and stretches will be undertaken. Here the amplitude of the EMG activation during each test relative to resting levels will be measured.

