9.3.2 Secondary Outcome Measures

- Walking Kinematic variability measured using PROMOVE inertial sensors over 6 Everyday Walking Tasks.
- SCALE Selective Control Assessment of the Lower Extremity
- Maximal Isometric and Isokinetic knee extensor strength using Dynamometer (Biodex system 2, Uk) of the most affected limb. Inner and outer range and maximal isokinetic strength.
- Maximal Isometric Knee Flexor Strength using dynamometer (Biodex system 2, Uk) of the most affected limb
- Knee flexor stiffness using dynamometer (Biodex system 2, Uk) of the most affected limb- passive and stretch reflex mediated stiffness and EMG amplitude post-fast stretch
- PROM of the ankle, in a flexed and extended knee position bilaterally using a goniometer
- Popliteal angle of the knee bilaterally using a goniometer

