10.4 Access to Data

Data will be collected and stored in accordance with the Data Protection Act 1998/General Data Protection Regulation 2018. Data generated from this study will be available for inspection on request by the participating research team, Plymouth University representatives, the REC, local R&D Departments and the regulatory authorities.

11. Statistics and Data Analysis

11.1. Analysis of Impairment:

Data will be assessed for normality using a Shapiro-Wilks test. People with CP with and without crouch gait will be compared to TDC using an Analysis of Variance. Significant data will be explored further with post-hoc testing. The following variables will be assessed:

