11.1.1 Strength

Isometric knee extensor strength (90 & 30 degrees); Inner and outer range ratio; maximal isokinetic knee extensor strength; maximal knee flexor strength. As strength measures will be related Bonferroni correction will be provided (n=5 variables p=0.05/5=0.001).

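### The Bonferroni divisor for stiffness is three, but the methods section counts four stiffness variables; whether total stiffness is tested must be settled when the printed threshold is corrected

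*Protocol*

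**What the plan says.** Protocol section 11.1 compares three groups (CP with crouch gait, CP without it, and typically developing children): "People with CP with and without crouch gait will be compared to TDC using an Analysis of Variance". Section 11.1.2 applies this to stiffness with a corrected threshold: "Passive stiffness total, stretch reflex mediated stiffness and EMG amplitude in the hamstrings will be analysed with a Bonferroni correction (n=3 variables". The same sentence prints that threshold as 0.05/3 = 0.0015.

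Section 7.3.2 defines the measures. Passive and total stiffness are determined separately: "Passive stiffness (assessed following the 5 deg/s stretch) and total stiffness following the fast stretch will be determined". The third is a difference of these two: "Stretch Mediated stiffness = Total stiffness (fast stretch)- passive stiffness". The section then counts them: "In total four variables will be assessed (Passive Stiffness, total stiffness, stretch mediated stiffness and EMG amplitude".

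The secondary outcomes in section 9.3.2 give a shorter list for the knee flexors: "passive and stretch reflex mediated stiffness and EMG amplitude post-fast stretch". Objective 5 (Trial Summary and section 9.2) and the predictor list in section 4 name only passive and stretch-mediated stiffness.

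**The concern.** A Bonferroni divisor should equal the number of tests in the family. Here one section counts four variables, and the analysis section divides by three over a list whose length depends on a comma. Read without the comma, its first item is a passive total stiffness that the protocol defines nowhere: in section 7.3.2 passive stiffness comes from the slow stretch and total stiffness from the fast one. Read with the comma, the list matches the four variables of section 7.3.2 in the same order, and the divisor is one short.

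At stake is which threshold applies to the secondary comparisons of stiffness between groups. The printed level has to be corrected in any case, and whoever corrects it needs to know the divisor. If the point stays open, the number of tests and the threshold can be settled after the data have been seen.

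**Working it through.** **Inputs.** Family-wise level 0.05, divisor 3 and printed level 0.0015 (section 11.1.2); count of 4 (section 7.3.2); list of 3 (section 9.3.2); one three-group ANOVA per variable (section 11.1).

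**The plan's own figure.** Bonferroni level = 0.05 / k.
- k = 3: 0.05 / 3 = 0.0167
- k = 4: 0.05 / 4 = 0.0125
- The printed 0.0015 would need k = 0.05 / 0.0015 = 33.3.

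The printed level therefore follows from neither count. The strength family has the same kind of slip ("As strength measures will be related Bonferroni correction will be provided (n=5 variables p=0.05/5=0.001"; 0.05 / 5 is 0.01). This division error is separate from the question of the divisor.

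**Counts side by side.**

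| Section | Passive | Total | Stretch-mediated | EMG amplitude | Count |
|---|---|---|---|---|---|
| 7.3.2 | yes | yes | yes | yes | 4, stated |
| 9.3.2 | yes | no | yes | yes | 3, by listing |
| 11.1.2 | yes | unclear | yes | yes | 3, stated; 3 or 4 by listing |

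The strength family shows how the protocol counts elsewhere. Section 11.1.1 lists isometric extensor strength at two angles, their ratio, isokinetic extensor strength and flexor strength, and sets n = 5. A derived variable (the ratio) counts there as a test, so being arithmetically related to other variables does not by itself remove total stiffness from its family.

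**Upper bound on family-wise error** (number of tests × level):

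| Level | 3 tests | 4 tests |
|---|---|---|
| 0.0015 (printed) | 0.0045 | 0.006 |
| 0.0167 (0.05/3) | 0.050 | 0.067 |
| 0.0125 (0.05/4) | 0.0375 | 0.050 |

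If the four tests were independent, the rate at 0.0167 would be 1 − (1 − 0.0167)^4 = 0.065.

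**Simulation under the null hypothesis.** Total stiffness is the sum of passive and stretch-mediated stiffness, so the four tests are not independent. Assumptions that the protocol does not give: groups of 10, 10 and 20; normal data; equal variances of the passive and mediated parts; EMG amplitude correlated 0.3 with passive and 0.5 with mediated stiffness. Rate at 0.0167, 30,000 runs for each setting:

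| Passive–mediated correlation | 4 tests |
|---|---|
| −0.3 | 0.058 |
| 0 | 0.056 |
| 0.3 | 0.052 |
| 0.5 | 0.050 |

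Over the same settings, the three tests without total stiffness give 0.046 to 0.047. With all three underlying variables uncorrelated (100,000 runs), four tests give 0.057 at 0.0167 and 0.043 at 0.0125.

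**The case against.** The strongest reply is that the analysis section agrees with itself. As printed, 11.1.2 has three items separated by commas and n = 3, and a comma lost in the PDF reading cannot be excluded. Most of the protocol points to three: total stiffness is missing from section 9.3.2, from objective 5 and from the predictor list in section 4. Section 7.3.2 describes measurement, and total stiffness may appear there only as the step from which the mediated part is derived.

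This stands as far as it goes. A reader might infer that four tests are definitely made and that the divisor is simply wrong; the documents do not establish that. If three tests are meant, n = 3 is right. The reply does not remove the conflict, though. Section 7.3.2 gives an explicit count of four, the word for total stiffness in 11.1.2 is unexplained on the literal reading, and section 11.1 uses the same verb (assessed) for the variables that it analyses.

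A second reply also stands: at the printed 0.0015, a p-value between 0.0125 and 0.0167 fails whichever count is meant. The divisor decides nothing until the division is corrected.

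A reader might further infer that testing total stiffness counts the same evidence twice, or adds nothing. Neither follows. Bonferroni holds under any dependence, and the redundancy pulls the error rate below the 6.7% bound. A separate test on a sum can also show what its parts do not: two uncorrelated parts of equal variance that each differ by 0.5 SD give a sum that differs by (0.5 + 0.5)/√2 = 0.71 SD.

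**Conclusion.** The point holds in conditional form. The divisor of three conflicts with the stated count of four unless total stiffness is left out of testing, and the protocol does not say that it is.

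The size is small. As printed there is no inflation, since the bound is at most 0.6%; the cost of 0.0015 is lost power, and it comes from the division error. Once the level is corrected to 0.0167, four tests would have a bound of 6.7% and a simulated rate of about 5 to 6%. The simulated figure rests on the assumed correlations, variances and 10/10 split of the CP group; the bound does not. In practice only a stiffness result with p between 0.0125 and 0.0167 would change status.

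Stiffness is one of the impairment categories that feed the regression, so a reader might infer that the threshold affects the main analysis. It does not: section 11.2.1 picks predictors by the largest difference between the two CP groups, not by a p-value. The effect is confined to secondary group comparisons.

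**What to change.** Make one edit to section 11.1.2, together with the correction of 0.0015. Name each tested variable, separated by commas, and match the divisor and the printed level to that list:

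- **Three tests:** passive stiffness, stretch-mediated stiffness and hamstring EMG amplitude, as in section 9.3.2; n = 3; level 0.05/3 = 0.0167. State that total stiffness is reported descriptively, and say so in section 7.3.2.
- **Four tests:** the same three and total stiffness; n = 4; level 0.05/4 = 0.0125. Add total stiffness to section 9.3.2.

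Either choice is sound if it is fixed before the data are analysed. Sections 7.3.2, 9.3.2 and 11.1.2 should then agree. The change is to wording only, with no effect on sample size or data collection. Under the first option total stiffness loses its own test; under the second the level is slightly stricter for the other three variables.

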11.1.3 PROM

Ankle range and popliteal angle.

11.1.4 SMC

SCALE is a summated ordinal measure. Therefore groups will be compared using a non-parametric Friedman's test.

11.3 Sample size calculation

Previous work has explored factors affecting stiffness gait in children with CP. Twenty Seven pwCP (age 13.6±8.3 years; gender 15 males, 12 females; height 1.4 ±0.2 metres [m]; weight 39.2± 19.4 kilograms [kg]) were compared to 20 controls. Marked differences in knee strength and stiffness (rectus femoris) were seen between TDC and children with CP with minimal effect sizes of 0.68 (range 0.68-2.2). With 18 people in each group it would be possible to detect a minimum effect size of 0.68. To account for 10% data loss in some measures (e.g. due to participants not completing some tests) we will recruit 20 people with CP and 20 people TDC. With 20 people with CP it will be possible to undertake a multiple regression to investigate factors associated with mean knee flexion amplitude during the EWT and up to two predictors (measures of impairment).

12.SAFETY AND MANAGEMENT OF RISK

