Crouch gait is the most common gait problem, affecting 72-76% of ambulant children with bilateral CP (Wren, Rethlefsen & Kay, 2005). This highly inefficient, tiring gait pattern is characterized by excessive knee flexion during stance phase of gait and if left untreated can lead to chronic knee pain (O'Sullivan et al., 2018). Once 30° knee flexion while walking is reached, the degree of crouch rapidly progresses leading to the child requiring wheelchair use for mobility (Galey et al., 2017). The cause of Crouch gait is unclear and is multifactorial in nature, with potential factors including but not limited to, knee extensors weakness , excessive tibial torsion, knee flexor spasticity and contracture and impaired Selective Motor Control (SMC) (O'Sullivan et al., 2018 , Kedem & Scher, 2016).

SMC is classified as a negative motor sign and when impaired it is defined as 'the inability to isolate the activation of muscles in a selected pattern in response to demands of a voluntary

posture or movement' (Sanger *et al.*, 2006). A recent cross-sectional study found a significant relationship between SMC, as measured by SCALE (Selective Control Assessment of the Lower Extremity), and knee flexion angle during both initial contact and midstance, in children with bilateral spastic CP (Zhou et al., 2018). This suggests that SMC may affect the ability of children with crouch gait to extend the knee during stance phase of gait, when the ankle is dorsiflexed (Zhou *et al.*, 2018). However, this study failed to include a measure of muscle strength, making it difficult to identify if SMC is affecting the ability of the knee to extend, when the ankle is dorsiflexed, or whether this simply due to the inability of weak knee extensor muscles to activate (Sanger *et al.*, 2006). In reality, due to the multifactoral nature of crouch a contribution of different neuromuscular impairments is likely. To examine this further, this observational study will explore how both SMC and knee extensor strength impact upon crouch gait.

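### Section 11.3 says 18 per group can detect an effect of 0.68; under conventional assumptions the power there is about 51%, and 80% power needs d = 0.96

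*Protocol*

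**What the plan says.** Section 11.3 draws on earlier work that compared 27 people with CP with 20 controls. It takes 0.68 as the smallest standardised difference in knee strength and stiffness, from a range of 0.68 to 2.2, and concludes: "With 18 people in each group it would be possible to detect a minimum effect size of 0.68". It then adds an allowance, "To account for 10% data loss in some measures", and arrives at the target: "we will recruit 20 people with CP and 20 people TDC". Power, significance level, sidedness, test and type of effect size are not given. For the regression, the section says only that 20 children with CP make a model with up to two predictors possible.

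The analysis that the figure supports is in Section 11.1: "People with CP with and without crouch gait will be compared to TDC using an Analysis of Variance", with post-hoc tests. Bonferroni thresholds follow in Section 11.1.1 ("n=5 variables p=0.05/5=0.001") and Section 11.1.2 ("n=3 variables p=0.05/3=0.0015"). Section 11.1.5 divides the children with CP into those with and without crouch gait by a midstance cut-off of 21 degrees, and Section 11.2 carries the three groups into a repeated-measures ANCOVA.

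**The concern.** A statement that a study can detect an effect is normally understood to mean 80% or 90% power. An effect of 0.68 with 18 per group is well short of that in an independent two-group comparison. This sentence is the only quantitative support in the protocol for recruiting 40 children. A reader who trusts it would expect a true difference of 0.68 to show up, when the chance of a significant result is close to even. The figure also concerns a contrast of two groups at an unadjusted level, whereas the plan has three groups and Bonferroni-adjusted families.

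**Working it through.** **Inputs.** From Section 11.3: effect 0.68, 18 evaluable per group, 10% loss, 20 recruited per group. From Section 11.1: independent groups. Assumed, because not stated: Cohen's d, two-sided alpha 0.05, target power 80%.

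**Step 1: the plan's own figures.** The allowance for loss reproduces: 18 / 0.9 = 20. The 0.68 does not reproduce as an effect detectable with 80% or 90% power. With 18 per group the smallest observed d that reaches p = 0.05 is

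t(0.975, 34 df) × √(2/18) = 2.032 × 0.333 = 0.677.

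The stated 0.68 coincides with that significance threshold. Whether it was obtained that way cannot be told from the text.

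**Step 2: power at d = 0.68.** The noncentrality is d × √(n/2), and power is the noncentral-t probability beyond the critical value. For n = 18: 0.68 × √9 = 2.04, against a critical value of 2.032.

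| n per group | Sidedness at alpha 0.05 | Power at d = 0.68 |
|---|---|---|
| 18 | two-sided | 51% |
| 20 | two-sided | 55% |
| 18 | one-sided | 64% |
| 35 | two-sided | 80% |

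For 80% power at 0.68, 35 per group are needed two-sided (34 by the normal approximation) and 28 one-sided.

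**Step 3: effect detectable with 80% power at 18 per group, two-sided.**

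| Alpha | Origin | Detectable d | Power at d = 0.68 |
|---|---|---|---|
| 0.05 | unadjusted | 0.96 | 51% |
| 0.0167 | stiffness, 0.05/3 | 1.13 | 33% |
| 0.01 | strength, 0.05/5 | 1.20 | 26% |
| 0.0015 | as printed, 11.1.2 | 1.45 | 10% |
| 0.001 | as printed, 11.1.1 | 1.50 | 8% |

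The two printed thresholds are not the quotients shown beside them: 0.05/5 is 0.01 and 0.05/3 is 0.0167.

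**Step 4: Crouch+ versus Crouch-.** The protocol fixes no split of the 18 to 20 children with CP, so a range is shown (80% power, two-sided 0.05).

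| Split | Detectable d |
|---|---|
| 10 v 10 | 1.32 |
| 12 v 8 | 1.35 |
| 9 v 9 | 1.41 |
| 14 v 6 | 1.45 |
| 15 v 5 | 1.53 |
| 13 v 5 | 1.57 |

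That is about 1.3 to 1.6. A still more uneven 14 v 4 would give 1.69.

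**Step 5: regression, as context.** For the overall F-test with two predictors at alpha 0.05, 80% power requires R² = 0.40 with n = 18 and 0.37 with n = 20.

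**Step 6: other readings of 0.68.** A paired test with a standardised mean difference of 0.68 and 18 pairs has 78% power (19 pairs reach 80%). Read as Cohen's f, 0.68 has 98% power with two groups or 95% with three equal groups (36 children in all), so it would not be the minimum detectable value.

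**The case against.** The protocol does not say what its sentence assumes, so calling it wrong depends on supplying the missing inputs. The paired reading comes close to 18, and the background does mention matched controls. This leaves the origin of 18 uncertain but does not rescue the claim. No matching procedure is described, the only inclusion criterion for the typically developing children is their age range, the earlier study compared unequal groups of 27 and 20, and Section 11.1 plans a between-group ANOVA.

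The effect of 0.68 is also the floor of the earlier range. With 18 per group, power is 83% at d = 1.0 and 99% at d = 1.5, so CP versus typically developing children is weak at the bottom of that range and not throughout. This stands.

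Three stronger readings may tempt a reader:

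- **That Crouch+ versus Crouch- can detect only d of about 1.5 or more.** This applies the background prevalence ("affecting 72-76% of ambulant children with bilateral CP") to a sample in which crouch is defined by the protocol's own cut-off. No split is fixed, and a balanced one gives 1.32. Section 11.1.5 also says differences between the crouch groups will be summarised descriptively, although Sections 11.1 and 11.2 test the same groups formally.
- **That the protocol makes a false power claim for its primary regression.** Section 11.3 says only that the regression can be undertaken. Nor should power for a single correlation stand in for the model. At the strength-gait correlations cited in the background (0.477 and 0.527), taking R² = r², the two-predictor F-test has about 45% to 62% power with n = 18 to 20.
- **That null results will be read as showing no difference.** Nothing in the protocol says so.

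**Conclusion.** The detectable-effect sentence in Section 11.3 is wrong for the comparison the protocol plans. Assuming Cohen's d, independent groups and two-sided alpha 0.05, power at 0.68 is about 51%, and the effect detectable with 80% power is 0.96, some 40% larger (0.96/0.68 = 1.41). A one-sided test raises power to only 64%, and the full 20 per group to 55% two-sided. The error lies in the stated property of the design and does not by itself make the sample of 40 unusable. The limits on the crouch contrast and the regression are real, but they belong beside the corrected figure as context: Section 11.3 does not claim that 0.68 covers them. That 0.68 was derived as a significance threshold is a plausible inference from the match with 0.677 and is not established.

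**What to change.** Keep 40 children and rewrite Section 11.3 as follows:

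1. State the effect-size type, test, alpha, sidedness and power.
2. Replace the 0.68 claim: 18 per group gives 80% power for d = 0.96 at two-sided 0.05, for d = 1.20 at 0.01 (strength) and for d = 1.13 at 0.0167 (stiffness).
3. In the same amendment, correct the printed thresholds in Section 11.1.1 (0.001 to 0.01) and Section 11.1.2 (0.0015 to 0.0167). Otherwise the new text would contradict them.
4. Say that the 0.68 from earlier work refers only to CP versus typically developing children.
5. Say that Crouch+ versus Crouch- detects d of about 1.3 to 1.6 at alpha 0.05, depending on the split. Label it exploratory and report it with 95% confidence intervals.
6. Add that a two-predictor regression in 18 to 20 children has 80% power only for R² of about 0.37 to 0.40.

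The cost is protocol wording and a less favourable stated figure. No additional children are needed. Holding to 0.68 with 80% power would instead take 35 evaluable per group, or 35/0.9 = 38.9, so 39 recruited per group.

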12.1. Dynamometer (Biodex, Suffolk UK)

The Study Co-ordinator will ensure that the Biodex (Suffolk,UK) is used and set up in accordance to the Standard Operating Procedure. This will ensure that it is set up correctly and will also include a manual handling assessment to help the participant safely transfer into the Biodex chair. Prior to Dynamometer set up a verbal explanation of how the Biodex works will be given to the participant and the parent and/or legal guardian. If the participant remains anxious or concerned, then the research assistant will demonstrate how it is used. The participant will also be made aware of the emergency stop button, so they can stop the Biodex dynamometer at any point. Prior to starting the Dynamometer measurements, the participant will be given the opportunity to ask questions. The Biodex has software and hardware safety features to prevent over stretching muscles and the dynamometer motor exerting too much torque.

